10.4. STATISTICAL METHODS FOR EXPLORATORY ENDPOINTS

Nasal polyps assessment:

Nasal polyps assessment will be performed at Screening (Visit 1) and at IP discontinuation/Week 24 (EOS) visits. Shift from baseline to Week 24/EOS in nasal polyps categories (Present, absent, missing/not assessed) will be presented.

Analysis of blood eosinophilis and Serum IgE(total):

Analysis of ratio to baseline in blood eosinophils and Serum IgE (Total) will be performed using a

mixed model repeated measures (MMRM) analysis as described in section 10.2.3 including visit, baseline maintenance OCS dose and asthma exacerbations in the year prior to the study (as an ordinal variable -0, 1, 2, 3+) as covariates. The analysis will be conducted using log_e scale transformed values for blood eosinophils. The model will be used to estimate the ratio to baseline at each scheduled visit with 95% confidence limits and corresponding p-value.

In addition, descriptive summaries will be presented for blood eosinophils and Serum IgE (Total) at each scheduled visits using number of subjects, geometric mean, geometric SD, median, minimum and maximum values.

10.5. SUBGROUP ANALYSIS

Subgroup analysis will be done according to subjects received OCS at baseline (yes, no).

10.6. MULTIPILICTY

There will be no hypothesis test is planned. Hence, no adjustment for the multiple comparison is required.

10.7. IMPUTATION OF MISSING DATA

Missing values will be treated as missing unless and otherwise specified. If a subject experience a clinically significant asthma exacerbation between Weeks 20-24, then for the purpose of assessing percentage of subjects achieving at least 50% reduction in OCS dose during the weeks 20-24, the subject will be imputed into the worst-case category of 'no reduction in OCS Dose'. For the analysis of median percent OCS reduction during weeks 20-24, the subject will be imputed using the maximum dose of OCS observed during the 4-Weekly period across all participating subjects.

11. SAFETY ANALYSIS STRATEGY

All analyses described in this section will be performed on the safety population. All safety analyses will be reported separately of the subjects receiving baseline OCS use (yes, no). The results will be descriptive in nature. Safety will be assessed based on the following assessments:

- Extent of Exposure
- Adverse Events

- Clinical Laboratory Evaluation
- Immunogenicity
- Vital Signs
- 12 Lead ECG
- Steroid toxicity and withdrawal

11.1. EXTENT OF EXPOSURE

The total exposure to mepolizumab is calculated as the date of last dose of mepolizumab minus the date of first dose of mepolizumab plus 29 minus periods of interruptions (in days). Subjects who entered into induction phase but did not report any treatment dates will be categorized as having zero days of exposure. The extent of exposure will be summarized as number of injections administered and number of days on treatment.

Interruption period is calculated as the date of dose of mepolizumab after interruption period minus the date of interruption period of mepolizumab or the date of missed dose of mepolizumab.

11.2. Adverse Events

The applicable definition of an Adverse Event (AE) is in the study protocol Sections 8.3 and 10.3. All AEs occurring from when a subject sign informed consent to when a subject exits the study will be accounted for in the reporting. AEs occurring pre-treatment, on-treatment and post-treatment periods will be summarized for the safety population.

A pre-treatment AE is defined as any AE with an onset date before the date of first exposure to the study drug. An on-treatment-AE is an event does not present prior to first exposure to the study drug or any pre-existing event that worsens following exposure to study drug until the last exposure to the study drug plus 28 days inclusive. Any AE which occurs after 28 days of last exposure to the study drug will be considered as post-treatment AEs. All AEs will be coded using the MedDRA central coding dictionary (26.0) and grouped by body system and preferred term. See Appendix 1 for imputation of partial dates for AEs. Imputed dates will be used to determine on-treatment status.

The following summaries will be generated for adverse events:

- AEs by treatment period (on and post-treatment), SOC and PT
- Common (>=3%) non-serious on-treatment AEs by SOC and PT

- AE occurred on the day of dosing by SOC and PT
- On-treatment drug-related AEs by SOC and PT
- AEs leading to permanent discontinuation or withdrawal from study by SOC and PT
- Serious AEs by treatment period (pre, on and post-treatment), SOC and PT
- Non-fatal SAE by treatment period (pre, on and post-treatment), SOC and PT
- Fatal SAE by treatment period (on and post-treatment), SOC and PT

Events with missing relationship to the study drug is considered as related. In addition, a summary of overall AEs during the study duration will be presented which includes:

- Subjects with at least one AE
- Subjects with at least one drug-related AE
- Subjects with AE leading to premature discontinuation
- Subjects with at least one serious AE
- Subjects with at least one drug-related serious AE
- Subjects with at least one AE leading to death
- Any on-treatment AEs
- Any on-treatment SAEs

The following listings will be generated:

- Listing of all Adverse Events
- Listing of Fatal Adverse Events
- Listing of Non-Fatal Serious Adverse Events
- Listing of Adverse Events Leading to Discontinuation of Investigational Product and/or Withdrawal from the Study

11.2.1. Adverse Events of Special Interest

Adverse events of special interest (AESIs) are adverse events associated with the identified and potential risks of mepolizumab. AESIs of systemic reactions (including systemic reactions meeting Sampson's criteria for anaphylaxis) and local injection site reactions are collected via targeted eCRF pages within the study. Events captured on the eCRF as systemic reactions will be further categorized by the investigator as 'allergic (type I hypersensitivity) reactions' or 'systemic other reactions. AESIs of opportunistic Infections, malignancies, serious cardiac, vascular and thromboembolic (CVT) events

and serious ischemic events will be identified using structured MedDRA query as defined in Appendix xx. The following AESIs will be summarized only for the on-treatment period:

- Events Reported by the Investigator as Systemic Reactions Allergic (Type I Hypersensitivity) by PT
- Events Reported by the Investigator as Systemic Reactions Other Reactions by PT
- Systemic Reactions Reported by the Investigator as Meeting the Criteria for Anaphylaxis by PT
- Events Reported by the Investigator as Local Injection Site Reactions by PT
- Potential Opportunistic Infections by PT
- Malignancies by PT
- Serious Cardiac, Vascular and Thromboembolic AE by PT
- Serious Ischemic AEs by PT

A subject listing will be provided for each of the AESI categories.

11.2.2. Cardiovascular Events

The following cardiovascular events will be captured on targeted CV event pages of the eCRF:

- Myocardial infarction/unstable angina
- Congestive heart failure
- Arrhythmias
- Valvulopathy
- Pulmonary hypertension
- Cerebrovascular events/stroke and transient ischemic attack
- Peripheral arterial thromboembolism
- Deep venous thrombosis/pulmonary embolism
- Revascularization

Counts and percentage of subjects with on-treatment cardiovascular events will be summarized. A subject listing will be provided.

11.2.3. Liver Events

A listing of all subjects with liver events will be presented with the following details:

- Time from the start of study treatment to the liver event and the time from the most recent study treatment to the liver event.
- Size, final diagnosis and abnormalities of liver biopsy.
- Alcohol intake and medical conditions at onset of liver event
- Liver imaging abnormalities

11.2.4. Steroid Toxicity and Withdrawal

Steroid toxicity and withdrawal will be summarized descriptively which includes:

- Prior duration of OCS use (<1 year, 1 to <5 years, 5 to <10 years, 10 to <15 years, 15 to <20 years, 20 to <25 years, >=25 years)
- Baseline optimized OCS dose both categorical (>0 5mg, >5 10mg, >10 15mg, >15 20mg, >20 25mg, >25 30mg, >30 35mg and >35mg).
- Baseline medical conditions specifically summarizing the status (past, current, no medical condition) of the following: hypertension, endocrine disorders, eye disorders, metabolism and nutritional disorders, nervous system disorders, and bone fractures.
- Observed and change from baseline in body weight at each visit
- Observed and change from baseline in glucose levels at each visit

11.2.5. Adverse Event Pertaining to COVID-19

A summary of on-treatment adverse events for subjects with COVID-19 suspected, probable and confirmed COVID-19 diagnosis by system organ class and preferred term will be presented.

11.3. CLINICAL LABORATORY EVALUATIONS

Clinical laboratory evaluations include hematology, clinical chemistry, and urinalysis. A list of laboratory assessments to be included in the outputs are given below:

Hematology: Hematocrit, Hemoglobin, Mean corpuscular hemoglobin (MCH), Mean corpuscular volume (MCV), Platelet count, Red blood cell (RBC) count, White blood cell (WBC) count, Neutrophils, Lymphocytes, Monocytes, Eosinophils, Basophils and Reticulocytes.

Clinical chemistry: ALP, ALT, AST, total bilirubin, direct bilirubin, Total Protein, Blood Urea Nitrogen, Creatinine, Glucose (non-fasting Random), Potassium, Sodium and Calcium.

Urinalysis: microscopy (epithelial cells, RBCs, pus cells (WBC), Dysmorphic RBC, casts, and crystals); and urine chemistry (specific gravity, pH, protein, glucose, bilirubin, urobilinogen, ketones and protein (Albumin))

Serology: Hepatitis B surface antigen (HBsAg) and Hepatitis C virus antibody.

The assessment timepoints for the laboratory parameters are provided in the following table.

| Laboratory Parameters | Assessment Time Points |
|-----------------------|--|
| Hematology | Screening (Visit 1), Week 0, Week 4, Week 8, Week 12, Week 16, Week 20, and Week 24 (EOS) |
| Clinical Chemistry | Screening (Visit 1), Week 0, Week 4, Week 8, Week 12, Week 16, Week 20, and Week 24 (EOS) |
| Urinalysis | Screening (Visit 1) |
| Serum IgE (total) | Pre-Screen, Screening (Visit 1) Week 0 |
| Serology | Screening (Visit 1) |
| Pregnancy Test | Screening (Visit 1), Week 0, Week 4, Week 8, Week 12, Week 16, Week 20, and Week 24 (EOS) |

If a laboratory value which is expected to have a numeric value for summary purposes, has a character value with '<x' or '>x', the number of significant digits in the observed values will be used to determine how much to add or subtract in order to impute the corresponding numeric value.

- Example 1: 2 Significant Digits = '<x' becomes x 0.01
- Example 2: 1 Significant Digit = '<x' becomes x 0.1
- Example 3: 0 Significant Digits = '<x' becomes x 1

Actual value and change from baseline (for quantitative measurements) will be summarized for hematology and clinical chemistry parameters at each scheduled visit. Shift from baseline to Week 24/EOS visits according to normal range criteria (for quantitative measurements) will be presented for hematology and clinical chemistry parameters. No summaries will be provided for urinalysis and serology parameter results.

A by-subject listings of all laboratory parameters will be provided which includes scheduled and unscheduled visits that clearly indicate the out of normal range values (where applicable) and possible abnormal values for the safety population.

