8.2.6. Clinical Safety Laboratory Assessments

- Refer to Appendix 2 for the list of clinical laboratory tests to be performed and to the SoA for the timing and frequency.
- The investigator must review the laboratory report, document this review, and record any clinically relevant changes occurring during the study in the AE section of the CRF. The laboratory reports must be filed with the source documents. Clinically significant abnormal laboratory findings are those which are not associated with the underlying disease, unless judged by the investigator to be more severe than expected for the participant's condition.
- All laboratory tests with values considered clinically significantly abnormal during participation in the study or within 7 days after the last dose of study intervention should be repeated until the values return to normal or baseline or are no longer considered significantly abnormal by the investigator or medical monitor.
- If such values do not return to normal/baseline within a period of time judged reasonable by the investigator, the aetiology should be identified and the sponsor notified.
- All protocol-required laboratory assessments, as defined in Appendix 2, must be conducted in accordance with the laboratory manual and the SoA.

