7. GENERAL ASPECTS FOR STATISTICAL ANALYSIS

7.1. GENERAL CONSIDERATIONS

Continuous data will be summarized using the number of subjects (n), arithmetic mean (mean), standard deviation (SD), median, minimum value (min), and maximum value (max) values unless otherwise specified. Categorical variables will be summarized using the frequency counts (n) and percentages (%) for each possible value. Where log-transformed data are used, the summary statistics will include geometric mean and geometric standard deviation (SD). Only data from protocol scheduled visits will be included in the summary tables. Data from unscheduled visits will not be included in the summary tables.

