| Visit 8 (Week 24) | 168 | 161 to 175 |

Unless otherwise stated, unscheduled visits will be included in the data listings only. If an unscheduled visit is present because of a visit/assessment missed due to COVID-19 factors, the unscheduled assessment may be used for remapping. The unscheduled visits may be used for summaries related to 'any time post baseline' assessment.

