| 14.3.3.3 | Summary of On-Treatment Adverse Events of Special Interest: Systemic Reactions Reported by the Investigator as Meeting the Criteria for Anaphylaxis (Safety Population) |
| 14.3.3.4 | Summary of On-Treatment Adverse Events of Special Interest: Events Reported by the Investigator as Local Injection Site Reactions (Safety Population) |
| 14.3.3.5 | Summary of On-Treatment Adverse Events of Special Interest: Potential Opportunistic Infections (Safety Population) |
| 14.3.3.6 | Summary of On-Treatment Adverse Events of Special Interest: Malignancies (Safety Population) |
| 14.3.3.7 | Summary of On-Treatment Adverse Events of Special Interest: Serious Cardiac, Vascular and Thromboembolic Adverse Events (Safety Population) |
| 14.3.3.8 | Summary of On-Treatment Adverse Events of Special Interest: Serious Ischemic Adverse Events (Safety Population) |
| 14.3.3.9 | Summary of On-Treatment COVID-19 Assessments for Subjects with Suspected, Probable or Confirmed COVID-19 Case Diagnosis by System Organ Class and Preferred Term (Safety Population) |
| 14.3.3.10 | Summary of On-Treatment All Cardiovascular Events Reported by the Investigator (Safety Population) |
| 14.3.4.1 | Summary of Hematology Parameters (Safety Population) |

| 14.3.4.2 | Summary of Clinical Chemistry Parameters (Safety Population) | |
|----------|---|--|
| 14.3.4.3 | Summary of Shifts from Baseline to Week 24/EOS in Hematology Parameters (Safety Population) | |
| 14.3.4.4 | Summary of Shifts from Baseline to Week 24/EOS in chemistry Parameters (Safety Population) | |
| 14.3.5.1 | Summary of Binding Anti-Drug Antibody (ADA) Assay: Highest Confirmatory Result (Safety | |
| | Population) | |
| 14.3.5.2 | Summary of Neutralizing Antibody Assay: Highest Result (Safety Population) | |
| 14.3.5.3 | Summary of Binding Anti-Drug Antibody (ADA) Assay: Highest Treatment Emergent Confirmatory | |
| | Result (Safety Population) | |
| 14.3.6 | Summary of Vital Signs Parameter Results (Safety Population) | |
| 14.3.7.1 | Summary of ECG Parameter Results (Safety Population) | |
| 14.3.7.2 | Summary of ECG Findings (Safety Population) | |
| 14.3.7.3 | Summary of Abnormal Values for ECG Parameters According to Range Criteria (Safety | |
| | Population) | |
| 14.3.8.1 | Summary of Steroid Toxicity and Withdrawal (Safety Population) | |
| 14.3.8.2 | Summary of Steroid Toxicity and Withdrawal: Serum Glucose and Body Weight (Safety | |
| | Population) | |

List of Figures

| Figure Number | Figure Title |

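### No planned table counts participants whose haematology or chemistry values left the normal range at any time on treatment; the shift tables use only Week 24/EOS

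*SAP*

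**What the plan says.** SAP 11.3 lists haematology and chemistry at screening, Week 0 and six post-baseline visits (Weeks 4, 8, 12, 16, 20 and 24). It plans descriptive summaries of values and changes at each scheduled visit. The only categorical laboratory summary is the shift: "Shift from baseline to Week 24/EOS visits according to normal range criteria (for quantitative measurements) will be presented for hematology and clinical chemistry parameters". SAP Appendix 5 carries this into Tables 14.3.4.3 ("Summary of Shifts from Baseline to Week 24/EOS in Hematology Parameters (Safety Population") and 14.3.4.4 ("Summary of Shifts from Baseline to Week 24/EOS in chemistry Parameters (Safety Population"). The other two haematology and chemistry tables, 14.3.4.1 and 14.3.4.2, are descriptive. None uses a worst value, any post-baseline value or a threshold.

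On unscheduled values, SAP 7.1 is unqualified: "Data from unscheduled visits will not be included in the summary tables". The visit-window text in SAP 7.2.8 sets a default, "Unless otherwise stated, unscheduled visits will be included in the data listings only", and then allows exceptions. Values may be remapped after premature withdrawal or when COVID-19 caused a missed assessment, and "The unscheduled visits may be used for summaries related to 'any time post baseline' assessment". No laboratory summary of that last kind is defined anywhere.

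Protocol 8.2.6 requires repeat testing for "All laboratory tests with values considered clinically significantly abnormal during participation in the study", or within 7 days after the last dose, until the value resolves or is no longer considered significant. Protocol Appendix 6 adds weekly or twice-weekly chemistry for liver events. Both rules generate unscheduled values.

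**The concern.** The primary objective is safety and tolerability, and a reader of the report will want to know how many participants went out of range on each parameter while on drug. The planned tables cannot answer that. The shift table uses one of six post-baseline visits. The by-visit summaries give n, mean, SD, median, minimum and maximum, so an extreme value can be seen but affected participants cannot be counted.

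Early stopping makes the gap wider. Protocol 7.1 asks sites to keep participants in the study after they stop drug, and SAP 7.2.4 ends the on-treatment period 28 days after the last dose. Someone who stops because of an abnormal result, recovers off drug and attends Week 24 enters the shift table with a value that does not describe treatment.

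The remapping exceptions do not close the gap. They send values to the next scheduled visit, which need not be Week 24. Whether an early end-of-study value belongs in the Week 24/EOS column is also not stated.

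**Working it through.** **1. Coverage, from the documents.** SAP 11.3 gives six scheduled post-baseline laboratory visits. One enters the shift table, so 5/6 = 83% of the scheduled post-baseline visits cannot contribute to it.

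**2. Early stopping, an example on the planned schedule.** Take a last dose at Week 8, which is 56 days after the first. The on-treatment period ends at 56 + 28 = 84 days. Week 24 is at 168 days, so the shift table uses a value 168 − 84 = 84 days after that period ended.

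**3. The plan's own detection figure.** SAP 5.3 justifies N = 100 by the chance of seeing at least one affected participant, 1 − (1 − p)^100. At p = 0.02 this is 1 − 0.98^100 = 0.8674, against 0.8673 stated. The rest of the table also reproduces, to within 0.0001.

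**4. Illustration for the shift table.** These assumptions are not in the documents: each affected participant has one abnormal episode covering m consecutive scheduled visits, with its start uniform over the six visits and runs cut off at Week 24. The episode is then present at Week 24 for m of the six possible starts. The share absent is 1 − m/6, and the chance that the Week 24 shift shows at least one affected participant is 1 − (1 − p·m/6)^100. At p = 0.02:

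| Visits abnormal (m) | Absent from Week 24 shift | p·m/6 | Chance of at least one in Week 24 shift |
|---|---|---|---|
| 1 | 5/6 = 83% | 0.00333 | 0.284 |
| 2 | 4/6 = 67% | 0.00667 | 0.488 |
| 3 | 3/6 = 50% | 0.01000 | 0.634 |
| 6 (persistent) | 0% | 0.02000 | 0.867 |

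An any-time table has 0.867 in every row. For m = 1 at risks of 5%, 3%, 2%, 1% and 0.5%, the Week 24 shift gives 0.567, 0.394, 0.284, 0.154 and 0.080. An any-time table gives 0.994, 0.952, 0.867, 0.634 and 0.394.

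**5. Price of a worst-value table.** Assume, again without support in the documents, that 5% of values per visit are out of range by chance, independently across six visits. Then 1 − 0.95^6 = 0.265, so about 26% of participants would show an out-of-range worst value on a given parameter. SAP 11.3 lists 13 haematology and 12 chemistry parameters, 25 in all.

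**The case against.** The strongest reply is that the report has other routes to these events.

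- Protocol 8.2.6 has investigators record clinically relevant laboratory changes as AEs, and Protocol 10.3.1 counts clinically significant abnormal results as AEs. They then appear in the AE tables by SOC and PT.
- For liver tests, Protocol Appendix 6 adds a liver event form and sponsor notification within 24 hours. Possible Hy's Law cases must be reported as SAEs, and SAP 11.2.3 plans a liver-event listing.
- The by-subject listings include unscheduled values, and Listing 16.2.8.1 isolates participants with any out-of-range value.
- When a scheduled visit triggers the repeats, the abnormal value itself stays in the by-visit summary. What is left out is mainly the follow-up.

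All of this stands. A reader might infer that transient abnormalities vanish from the report, or that only a listing would show them; the documents do not support that. Nor does the repeat-testing rule show that abnormalities are usually gone by Week 24. It covers only results judged clinically significant, and it gives no durations.

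What the reply does not supply is a participant count. The AE route depends on investigator judgement, minima and maxima do not count people, and listings are not summaries.

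The reply also notes that, with no comparator, a worst-value table collects chance abnormalities. That is a fair cost, and the reason to keep the Week 24 table.

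**Conclusion.** The gap is real and limited: the SAP has no tabulated count of participants with any on-treatment laboratory shift, and a resolved abnormality reads as normal-to-normal in the tables it does have. This is a cheap improvement to a supporting safety summary.

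It would be wrong to conclude that the primary analysis is compromised. The primary estimand is the incidence of AEs, SAEs and AESIs, and it does not use the shift tables. It would also be wrong to read 83% as the share of abnormalities the trial will miss. That figure describes one table, for one-visit episodes with uniform onset; persistent abnormalities are fully captured.

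Nor does the SAP breach the protocol, since Protocol 9.4.1 asks only that laboratory data be summarised. Its intention to report all data collected does, however, fit poorly with excluding unscheduled values by default. The SAP already goes further elsewhere: 11.6 counts QT categories at every visit, and 11.4 reports the highest post-baseline antibody result.

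**What to change.** - Add two tables, one for haematology and one for chemistry, of shift from baseline to the worst post-baseline on-treatment value, with high and low directions shown separately. Use scheduled, unscheduled and early-withdrawal values.
- Define on-treatment by SAP 7.2.4, and say where values more than 28 days after the last dose go. The discontinuation visit can fall at 28 + 7 = 35 days.
- Keep Tables 14.3.4.3 and 14.3.4.4 alongside, and state whether an early end-of-study value enters the Week 24/EOS column.
- Reconcile SAP 7.1 with SAP 7.2.8 so that unscheduled values may feed the new tables.

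The cost is two tables and a few sentences, with no new data, visits or change in sample size. The downside is more chance out-of-range results, about 26% of participants per parameter under the assumption in the working. A footnote should say that the worst-value shift is to be read with the Week 24/EOS shift.
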